### **2.3 Hypothesis**

This is an exploratory study and no hypothesis testing will be examined.

### **2.4 Risk-Benefit Assessment**

A patient with peanut allergy may or may not benefit from participating in this study. However, based upon the inhibition of IL-33 by the investigational product (IP) and pre-clinical study results, patients with peanut allergy may benefit. Participation in this study may help develop important scientific knowledge that could contribute to the development of a new medication and better comprehensive treatment of patients who suffer from AD, asthma, and food allergies.

ANB020 has been extensively tested in animals, and was found to be safe and well tolerated in a Phase I SAD study (ANB020-001) in healthy subjects. In animal studies, there were no ANB020 related adverse events (AEs) or abnormal ECG findings and the administration of ANB020 had no effect on hematology, coagulation, clinical chemistry, or urinalysis test results. In the SAD study, 64 healthy subjects were enrolled and dosed. The doses implemented in the SAD study were 10, 40, 100, and 300 mg SC and 40, 100, 300, 750 mg IV. No change in vital signs (BP, HR, ECG, or body temperature) was noted. Hematology parameters, such as erythrocytes, WBC, and platelet counts, were all within the normal range except for one subject in the 750 mg dose group. All others did not show any modification or trend related to ANB020 administration. Serum chemistry results were also all in the normal range. The most commonly reported TEAEs were upper respiratory tract infection (50% versus 48% in placebo and ANB020 group, respectively) and headache (32% versus 27% in placebo and ANB020 group, respectively) of mild to moderate intensity. No AEs were deemed by the Principal Investigator (PI) to be related to ANB020. Of all the AEs reported across all dose groups, 44% were reported as possibly related and 36% were reported as unrelated. One SAE of decreased neutrophils was reported in the 750 mg dose group which resolved without sequelae prior to study completion. No other observations of decreased neutrophils were observed. No dose dependent AEs were reported.

Although nothing in the testing of ANB020 to date indicates that an allergic reaction is likely; a reaction to any drug is possible. Some symptoms of allergic reactions are rash, wheezing or difficulty breathing, dizziness or fainting (also a possible outcome of a drop in BP), swelling around the mouth, throat or eyes, a fast pulse, or sweating.

As ANB020 is a mAb, based on clinical studies with other mAbs, study participants may experience symptoms of an apparent allergic reaction to the drug, also known as 'cytokine release syndrome'. The symptoms of this vary dramatically but can include:

- Mild to moderate fever, chills, headache, nausea, and vomiting.
- Moderate to severe symptoms such as edema, hypotension, and pulmonary infiltrates (e.g., blood and mucus in the lung).

## **3.0 STUDY OBJECTIVES**

### **3.1 Primary Objectives**

The primary objectives of the study are as follows:

- To assess the safety and tolerability of single dose administration of ANB020 in adult patients with peanut allergy.
- To measure the response of adult patients with peanut allergy on Day 14 following an oral blind placebo-controlled food challenge (BPCFC) threshold and total cumulative peanut dose tolerated after administration of ANB020 or placebo compared to cumulative baseline BPCFC.

### **3.2 Secondary Objectives**

The secondary objectives of the study are as follows:

- To compare the symptoms to peanut antigen challenge on Day 14 using the Oral Food Challenge (OFC) Symptoms Scoring Assessment Tool after administration of ANB020 or placebo compared to baseline peanut BPCFC symptoms.
- To describe the limited PK of ANB020 following a single, IV dose.

### **3.3 Exploratory Objectives**

- To assess the effect of ANB020 on circulating serum cytokines.
- To assess the effect of ANB020 on leukocytes within whole blood.
- To compare the immune response of ANB020 to placebo dosed patients in the ex vivo peanut antigen challenge. (Stanford University Only)
- To measure the response of adult patients with peanut allergy on Day 45 following an oral BPCFC threshold and cumulative peanut dose tolerated after administration of ANB020 or placebo compared to cumulative baseline peanut BPCFC.
- To compare the symptoms to peanut antigen challenge on Day 45 using the OFC Symptoms Scoring Assessment Tool after administration of ANB020 or placebo compared to baseline peanut BPCFC symptoms.

## 4.0 INVESTIGATIONAL PLAN

### 4.1 Summary of Study Design

This is a Phase II, double-blind, placebo-controlled, proof of concept study to assess the safety and tolerability of ANB020 in adult patients with peanut allergy. This study will also investigate the effects of ANB020 or placebo in adult peanut allergic patients following an oral BPCFC at 2 and 6 weeks post ANB020 or placebo administration. The effects of ANB020 on the immune response to peanut upon ex vivo peanut antigen challenge will be evaluated in Stanford University patients only.

Informed consent must be obtained prior to participation in the study. At the screening visit (7-21 days before Day 1), inclusion/exclusion criteria is assessed, each eligible patient will be administered a graded peanut and placebo oral food challenge (BPCFC) according to the PRACTALL consensus report (See [Section 6.1.1](#)). Vital signs, physical examination findings, and subjective symptoms during the BPCFC will be monitored per PRACTALL guidelines using the OFC Symptom Scoring Assessment Tool (See [Section 6.1.2](#)). The oral challenge should be stopped when the patient develops clinically significant symptoms indicative of an allergic reaction as per the Investigator's assessment. The total cumulative dose of blinded peanut/placebo tolerated during the dosing threshold challenge will be recorded. Patients will be observed until the Investigator determines that the patient is clinically stable and can be discharged. The oral food challenge can be completed in 2 days if the Investigator feels that it is the best for patient's safety and convenience. Otherwise all patients will undergo the peanut challenge and placebo challenge on the same day. If the Investigator is planning to complete the challenge (BPCFC) in 2 days, he or she needs to follow the procedures and assessments pertaining to the challenge on both the days as detailed in [Section 6.1.1](#), [6.1.2](#), and [7.1.3](#). Blood samples collected from Stanford University patients for pharmacodynamic (PD) assessments (ex vivo whole blood peanut antigen challenge) will be collected at screening (prior to BPCFC) to determine the intensity of the response and establish a baseline value of peanut antigen induced immune activation. Medical history and various other safety assessments including laboratory and biomarker analysis (cytokines) will be performed.

On Day 1, the patients will return to the study center and the assessment for inclusion and exclusion criteria will be reviewed. Eligible patients will be randomized to receive one intravenous dose of either ANB020 (300 mg/100 mL) or placebo (0.9% sodium chloride [100 mL]) in a 3:1 ratio. Specific laboratory and safety assessments will be performed. Serial samples for PK analysis will be collected according to [Section 18.0](#). Patients with any ongoing AEs or SAEs at the time of scheduled discharge from the study center should remain at the study center until the Investigator has determined that these events have been resolved or deemed as not clinically significant by the Investigator.

On Day 2 and Day 5, the patients will return to the study center and the samples for PK, biomarker analysis (cytokines), and whole blood for leukocytes will be collected, and other safety assessments will be performed. In addition, whole blood samples from Stanford University patients for ex vivo peanut antigen challenge assay will be obtained to determine the peanut antigen induced activation.

[figure not shown]
On Day 14, the patients will return to the study center and the oral BPCFC will be administered. Symptoms will be monitored using the OFC Symptom Scoring Assessment Tool and other safety assessments will be performed. The oral challenge should be stopped when the patient develops clinically significant symptoms indicative of an allergic reaction as per the Investigator's assessment. The total cumulative dose of blinded peanut/placebo tolerated and dosing step/threshold reached prior to reaction will be recorded. Patients will be observed until the Investigator determines that the patient is clinically stable and can be discharged. The oral BPCFC (peanut challenge and placebo challenge) can be completed in 2 days (one challenge on Day 14 and the second challenge on Day 15) if the Investigator feels that it is the best for patient's safety and convenience. Otherwise all patients will undergo the challenges (peanut challenge and placebo challenge) on Day 14 itself.

On Day 15, patients will visit the study center and the laboratory and safety assessments will be performed. The oral food challenge will be continued on Day 15 if the patient has received only the placebo challenge on Day 14 and the blood samples scheduled on Day 15 will be collected on Day 16 (only applicable if the Investigator decides to complete the challenge in 2 days). The Investigator must follow the procedures and assessments pertaining to the challenge on both Day 14 and Day 15 as detailed in [Section 6.1.1, 6.1.2, and 7.1.3](#). After completing the oral food challenge, all patients will be in the follow-up period for 30 days. During the 30 days follow-up period, the patients will be contacted weekly via telephone by study staff to assess the patient's well-being.

On Day 45, the patients will return to the study center for the End of Study (EOS) visit. If any objective reaction occurred at Day 14/15, the BPCFC (peanut and placebo oral food challenge) will not be required but may be performed at the discretion of the Investigator. If the Investigator decides to perform the challenge, the procedures will be the same as the Day 14/15 visit. The BPCFC may be performed on Day 45 according to the PRACTALL guidelines. Symptoms will be monitored using the OFC Symptom Scoring Assessment Tool and other safety assessments will be performed. The oral challenge should be stopped when the patient develops clinically significant symptoms indicative of an allergic reaction as per the Investigator's assessment. The total cumulative dose of blinded peanut/placebo tolerated and dosing step/threshold reached prior to reaction will be recorded. Patients will be observed until the Investigator determines that the patient is clinically stable and can be discharged. The oral BPCFC (peanut challenge and placebo challenge) can be completed in 2 days (one challenge on

Day 45 and the second challenge on Day 46) if the Investigator feels that it is the best for patient's safety and convenience. Otherwise all patients will undergo the challenges (peanut challenge and placebo challenge) on Day 45 (EOS visit) itself. Other procedures scheduled for the EOS visit will also be performed on Day 45. The study design is presented in [Figure 4.1](#) and the Schedule of Events is presented in [Table 4.1](#).

**Figure 4.1 Schematic of Study Design for Protocol ANB020-003**

Abbreviations: BPCFC = Blind placebo-controlled food challenge; PK = pharmacokinetics; n = sample size

\*Oral BPCFC will be continued on Day 15 if the patient has received only the placebo challenge on Day 14.

\*\*If the BPCFC continued on Day 15, the blood samples scheduled on Day 15 will be collected on Day 16.

^If objective reaction occurs on Day 14/15, the Oral BPCFC will not be required but may be performed at the discretion of the Investigator

^^Oral BPCFC will be continued on Day 46 if the patient has received the placebo challenge Day 45/EOC visit.

^^^If the BPCFC continued on Day 46, all assessments related to the BPCFC will be performed on Day 46. Concomitant medications and adverse events will also be recorded on Day 46. All laboratory/diagnostic tests scheduled for the EOC visit will be performed on Day 45. (See Table 4.1).

**Table 4.1 Schedule of Events**

Assessment Days	Screening 7-21 days prior to Day 1	Day 1	Day 2	Day 5	Day 14	Day 15	Follow-Up(30 days) Weekly Telephonic Contacts	EOS Day 45	EOS Day 46 n	ET f,p
General Assessments										
Informed Consent	X q	X a								
Medical History/Demographics	X									
Inclusion/Exclusion Criteria	X	X								
Oral Peanut Food Challenge (BPCFC)	X				X	X l,k		X l	X l,o	
Stanford University Only: Ex vivo Peanut Challenge Assay (whole blood) e	X		X	X						
Skin Prick Test and ImmunoCAP Testing	X h									
Safety Assessments										
Physical Examination b	X				X	X l		X	X l	X
Safety Laboratory c	X	X	X		X			X		X
Vital Signs b	X	X	X	X	X	X		X	X l	X
Spirometry or Peak Flow for Patients with History of Asthma i	X				X	X l,j		X l	X l,j	
Urinalysis	X	X	X		X				X	
Serum Pregnancy Test (WOCBP Only)	X	X			X			X		X
FSH m	X l									
12-Lead ECG	X							X		X
Concomitant Medications	X	X	X	X	X	X	X	X	X l	X
Adverse Events	X	X	X	X	X	X	X	X	X l	X
Clinical Observations										
Clinician and Patient Reported Outcomes (OFC Symptom Scoring Assessment Tool )	X				X	X l		X	X l	
PK/Biomarker Assessments										
Samples for PK d		X	X	X		X k		X		X
Serum Sampling for Biomarkers Cytokines e (IL-33, IL-4, IL-5, IL-9, IL-13, sST2)	X		X	X		X k				
Whole Blood for Leukocytes e	X g		X g	X		X k		X g		X g
IP administration										
Administration of ANB020 or Placebo		X								

Abbreviations: BPCFC = Blind placebo-controlled food challenge; ECG = electrocardiogram; EOS: End of Study; ET = Early Termination; FSH = follicle stimulating hormone; IL = interleukin; IP = investigational product; OFC = Oral Food Challenge; PK = pharmacokinetics; WOCBP = Women of childbearing potential

- a Confirm informed consent and continued willingness to participate.
- b See [Section 6.1.1](#) and [7.1.3](#) for the instructions to record vital signs, physical examination, and clinical evaluations using the OFC Symptom Scoring Assessment Tool during BPCFC.
- c See [Table 7.1](#) for safety laboratory details (Virology, Quantiferon Gold® test, and drugs of abuse to be performed at screening only).
- d See [Section 18.0 \(Appendix 2\)](#) for schedule of PK collection time points.
- e See [Section 18.0 \(Appendix 2\)](#) for schedule of peanut challenge assay, biomarker cytokines, and whole blood for leukocytes collection time points. During screening the samples for ex vivo peanut antigen challenge, whole blood for leukocytes, and serum samples for cytokines should be collected prior to administration of BPCFC. If necessary, the sample for ex vivo peanut antigen challenge can be collected on Day 1(instead of Screening), prior to dosing. **Ex vivo Peanut challenge is for Stanford University only.**
- f ET visit will include all procedures to be done at EOS visit as well as any procedures that should be done at the next regularly scheduled visit. ET visit will be performed if the patient discontinues the study before EOS visit. If the patient completes all study visits and return to study center for EOS visit on Day 45, ET visit will not be applicable.
- g Leukocytes will be obtained as part of hematology safety laboratory panel at screening, Day 2, and Day 45/ET. On Day 5 and Day 15, whole blood samples for leukocytes will be collected separately as there is no safety laboratory assessment on Day 5 and Day 15.
- h Only conduct skin prick test and ImmunoCAP testing if these tests had not been performed within 8 weeks before screening.
- i For patients with a history of asthma, spirometry or peak flow will be obtained before starting the initial placebo challenge and again before starting the initial peanut challenge . See [Section 6.1.1](#).
- j Only applicable if the Investigator decides to complete the oral food challenge in 2 days. See [Section 6.1.1](#) and [7.1.3](#) for the instructions to record vital signs, physical examination, and clinical evaluations using the OFC Symptom Scoring Assessment Tool during BPCFC.
- k If the Investigator decides to complete the BPCFC on Day 15, the blood samples for leukocytes (whole blood), biomarker analysis (cytokines), and PK analysis should be collected on the following day (Day 16). The patient's vital signs, adverse events, if any, and concomitant medications will also be recorded on Day 16.
- l If any objective reaction occurred at Day 14/15, the BPCFC (peanut and placebo oral food challenge) will not be required but may be performed at the discretion of the Investigator
- m The FSH levels will be obtained only on postmenopausal patients defined as aged over 45 years with at least 1 year of amenorrhea. Blood samples to determine the FSH levels will be obtained only at screening.
- n If the Investigator decides to complete the oral food challenge over two days, please refer to Day 46 and appropriate footnotes for guidance.
- o If the BPCFC is continued on Day 46, all assessments related to the BPCFC will be performed on Day 46. Concomitant medications and adverse events will also be recorded on Day 46. All laboratory/diagnostic tests scheduled for the EOS visit will be performed on day 45.
- P If the patient's ET visit is between Day 35 to 45, and the termination is for non-medical reasons, the BPCFC will be administered during the ET visit. If the ET visit is before Day 35, the BPCFC will not be repeated.
- q Informed consent must be obtained prior to participation in the study.

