#### **6.2.5 End of Study**

After the follow-up period, all patients will return to the study center for the EOS visit on Day 45. If any objective reaction occurred at Day 14/15, the BPCFC will not be required but may be performed at the discretion of the Investigator on Day 45 and the symptoms will be monitored (See [Section 6.1.1](#) and [Section 6.1.2](#)). If the Investigator decides to perform the BPCFC, it can be completed in 2 days (one challenge on Day 45 and the second challenge on Day 46) if the Investigator feels that it is the best for patient's safety and convenience. Otherwise all patients will undergo the challenges (peanut challenge and placebo challenge) on Day 45 (EOS visit) itself. All blood samples scheduled for the EOS visit will be collected on Day 45 (EOS visit) regardless of splitting the BPCFC assessments. Additional procedures will be carried out in accordance with the Schedule of Events in [Table 4.1](#).

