### 7.1.3 Vital Signs, Physical Findings, and Other Safety Assessments

Vital signs will be measured, and physical examinations and ECGs will be performed at the time points indicated in the Schedule of Events (Table 4.1).

Vital signs include pulse rate, respiratory rate, body temperature, systolic BP, and diastolic BP. The physical examination includes evaluation of general appearance, head, eyes, ears, nose, and throat, and pulmonary, cardiovascular, gastrointestinal, renal/genitourological, endocrine (including thyroid), musculoskeletal/spinal, lymphatic, and dermatologic systems.

During the BPCFC, clinical evaluations using the OFC Symptom Scoring Assessment Tool and vital signs will be done before starting the initial placebo challenge, after completion of the final placebo challenge, before starting the initial peanut challenge, upon completion of the final peanut challenge, and 2 hours after completion of the final peanut challenge. Full physical examinations will be performed before starting the initial placebo food challenge and upon completion of the final peanut challenge (prior to discharge), and more frequent if deemed appropriate by the Investigator on the challenge day.

A standard 12-lead ECG will be performed by a qualified physician or nurse. The following parameters will be documented: HR, PR interval, QRS interval, QT interval, and QTc interval. The ECG will be reviewed by the Investigator or an authorized representative who is experienced in the evaluation of ECGs and assessed for clinical significance.

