##### 3. Figure 4.1: Schematic of Study Design for protocol ANB020-003 –Page 24:

a. Description of Change: Changing screening period to 21 days

Purpose of Change: Allow time and flexibility for screening procedures

- b. Description of Change: Remove the requirement of the Day 45 BPCFC if an objective reaction occurred at Day 14/15.  
Purpose of Change: For patient safety, not requiring the Day 45 BPCFC if a reaction was observed at the Day 14/15 BPCFC. The investigator may decide to conduct the BPCFC per his/her discretion.
  - c. Description of Change: Changed “either peanut or placebo” to placebo.  
Purpose of Change: To clarify that subjects would receive placebo challenge first.
4. Table 4.1: Schedule of Events – Page 25, 26:
  - a. Description of Change: Changing screening period to 21 days  
Purpose of Change: Allow time and flexibility for screening procedures
  - b. Description of Change: Add “Informed consent must be obtained prior to participation in the study.”  
Purpose of Change: To clarify the Informed consent can be obtained prior to the screening visit.
  - c. Description of Change: Remove the requirement of the Day 45 BPCFC if an objective reaction occurred at Day 14/15.  
Purpose of Change: For patient safety, not requiring the Day 45 BPCFC if a reaction was observed at the Day 14/15 BPCFC. The investigator may decide to conduct the BPCFC per his/her discretion.
5. Section 6.0: Study Procedures – Page 37:
  - a. Description of Change: Change the visit window to + 4 days for Day 14/15.  
Purpose of Change: To provide flexibility to accommodate subject schedules.
6. Section 6.1: Screening – Page 37:
  - a. Description of Change: Add “Informed consent must be obtained prior to participation in the study.”  
Purpose of Change: To clarify the Informed consent can be obtained prior to the screening visit.
7. Section 6.2.3: Day 2 to Day 15 – Page 40:
  - a. Description of Change: Changed “either peanut or placebo” to placebo.  
Purpose of Change: To clarify that subjects would receive placebo challenge first.
8. Section 6.2.5: End of Study – Page 41:
  - a. Description of Change: Remove the requirement of the Day 45 BPCFC if an objective reaction occurred at Day 14/15.

Purpose of Change: For patient safety, not requiring the Day 45 BPCFC if a reaction was observed at the Day 14/15 BPCFC. The investigator may decide to conduct the BPCFC per his/her discretion.

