17.3.3. ANALYSIS OF EXPLORATORY EFFICACY ENDPOINTS

The Full Analysis Set will be used for the efficacy analysis.

The actual and change from baseline values of all the exploratory endpoints will be summarized using appropriate descriptive statistics by treatment at all time points where assessment is done. Change from baseline will be evaluated where possible.

Change from baseline on day 45 for tolerated dose and OFC symptom scores will be compared between ANB020 and placebo using a mixed model for repeated measures with treatment, visit, and treatment by visit interaction as fixed effect, and baseline and baseline by visit terms as covariates. The data collected at baseline, day 14, and day 45 will be used in the model.

The following statistics will be presented:

- o Treatment differences
- o Standard error of treatment difference
- o 95% CI
- o p-value

Document: \\ieedc-nas01a\biosdata\AnaptysBio\ANB020\CYA74393\Biostatistics\Documentation\SAP\Final2018-02-07
Author: [REDACTED] Version Number: Final 1.0
Version Date: 07Feb2018

Template No: CS_TP_BS016 Revision 4
Effective Date: 01Apr2016

Reference: CS_WI_BS005

STATISTICAL ANALYSIS PLAN

AnaptysBio Inc
PROTOCOL ANB020-003
Page 25 of 36

An appropriate covariance matrix (e.g., unstructured [UN]) will be used in the model.

The treatment difference and 95% CI will also be presented graphically.

Patient-wise data listings will be provided.

For analysis of exploratory PD endpoints, refer [Section 20](#) for details.

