Document: \\ieedc-nas01a\biosdata\AnaptysBio\ANB020\CYA74393\Biostatistics\Documentation\SAP\Final\2018-02-07

Author: [REDACTED]

Version Number: Final 1.0

Version Date: 07Feb2018

Listing Shells

AnaptysBio Inc.
PROTOCOL ANB020-003
Page 20 of 41

Listing 16 2 4 9
Prior and Concomitant Medications - Safety Analysis Set

Patient No / Treatment	Age/ Gender	Medication Number	Medication Name Reported/ Preferred Term	Start Date/ End Date/ Ongoing	Dose (Unit)/ Frequency/ Route	Indication	Prior or Concomitant
XXX/XXX	32/ Male	1	XXXX	DDMMYYYY/ DDMMYYYY	XXX mg	XXXX	Concomitant
XXX/XXX	31/ Female	2	XXXX	DDMMYYYY/ DDMMYYYY	XXX mcg	XXXX	Prior
XXX/XXX	28/ Female	3	XXXX	DDMMYYYY/ DDMMYYYY	XXX ml	XXXX	Prior
...							

Programming Note (not part of table): Sort by patient number, medication number, start date

Document: \\ieedc-nas01a\biosdata\AnaptysBio\ANB020\CYA74393\Biostatistics\Documentation\SAP\Final\2018-02-07

Author: [REDACTED]

Version Number: Final 1.0

Version Date: 07Feb2018

Listing 16 2 5 1
Exposure to Investigational Product – Safety Analysis Set

Patient No / Treatment	Age/Gender	IP administered via IV/ If No, reason	Start Date and Start Time	End Date and End Time	Total Volume Administered (mL)	If Total volume administered <100 mL, Reason
XXX/XXX	32/Male	Yes	DDMMYY YYYYThh:mm	DDMMYY YYYYThh:mm	XXXX	xxxx
XXX/XXX	31/Female	Yes	DDMMYY YYYYThh:mm	DDMMYY YYYYThh:mm	XXXX	-
XXX/XXX	28/Female	No/ xxxx				
...						

Note:

IP – Investigational Product
IV – Intravenous

Programming Note (not part of table): Sort by patient number, start date, start time

Document: \\ieedc-nas01a\biosdata\AnaptysBio\ANB020\CYA74393\Biostatistics\Documentation\SAP\Final\2018-02-07

Author: [REDACTED]

Version Number: Final 1.0

Version Date: 07Feb2018

Listing Shells

AnaptysBio Inc.
PROTOCOL ANB020-003
Page 22 of 41

Listing 16 2 6 1
Oral Peanut Food Challenge (BPCFC) - Full Analysis Set

Patient No / Treatment	Age/ Gender	Visit	Was oral BPCFC performed?	Cumulative Ingested 1 (Unit)	Start Date/ Start Time of dose challenge 1	End Date / End Time of dose challenge 1	Cumulative Ingested 2 (Unit)	Start Date/ Start Time of dose challenge 2	End Date / End Time of dose challenge 2
XXX/XXX	32/ Male	Baseline	Yes	XX	DDMMYY YYYYTh h:mm	DDMMYY YYYYTh h:mm	XX	DDMMYY YYYYTh h:mm	DDMMYY YYYYTh h:mm
		Day 14	-----						
		Day 45							
XXX/XXX	31/ Female	-----	No	XX	DDMMYY YYYYTh h:mm	DDMMYY YYYYTh h:mm	XX	DDMMYY YYYYTh h:mm	DDMMYY YYYYTh h:mm
XXX/XXX	28/ Female	-----	No	-	-	-	-	-	-

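### Unprovoked Day 45 OFC scores from Day 14/15 reactors who are not rechallenged can enter the exploratory Day 45 model and bias it against ANB020

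*Protocol*

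**What the plan says.** **Protocol, the challenge.** Footnote l of Table 4.1 reads: "If any objective reaction occurred at Day 14/15, the BPCFC (peanut and placebo oral food challenge) will not be required but may be performed". The decision is left to the investigator. The Summary of Changes for Amendment 5 (01 Dec 2017) records the change: "Remove the requirement of the Day 45 BPCFC if an objective reaction occurred at Day 14/15". The Synopsis and Sections 4.1 and 6.2.5 carry the same rule.

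**Protocol, the score.** In the extracted Table 4.1 the Day 45 cells for the challenge and for spirometry carry footnote l. The Day 45 cell in the row "Clinician and Patient Reported Outcomes (OFC Symptom Scoring Assessment Tool" is a plain X. The text is different:
- Section 7.1.3: "During the BPCFC, clinical evaluations using the OFC Symptom Scoring Assessment Tool and vital signs will be done before starting the initial placebo challenge". Its remaining scoring times are also placed around the placebo and peanut challenges, and Section 6.1.1 gives the same times.
- Section 6.2.5 names symptom monitoring in the same sentence as the optional challenge: "may be performed at the discretion of the Investigator on Day 45 and the symptoms will be monitored".

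**SAP.** Section 1 names Amendment 3 (30 Jun 2017) as the reference protocol, although the SAP is dated 07 Feb 2018. For the Day 45 tolerated dose and OFC scores, Section 17.3.3 says: "The data collected at baseline, day 14, and day 45 will be used in the model". It does not require that a challenge took place. Section 7.3 imputes nothing. The Full Analysis Set needs post-baseline challenge and OFC results, which the Day 14 visit already supplies. Listing 16.2.6.1 has a column "Was oral BPCFC performed", but no analysis rule uses it.

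**The concern.** An OFC score measures response to peanut only if peanut was given. Inclusion requires a positive reaction at the screening challenge, so a post-peanut baseline score reflects a real reaction. A Day 45 score from a patient who was not rechallenged should be near zero whatever that patient's sensitivity.

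Whether the challenge is skipped depends on a post-randomisation outcome, the Day 14/15 reaction, which the drug is meant to change. If ANB020 works, more of the placebo arm reacts at Day 14 and becomes eligible to skip. The placebo arm then collects more artificial zeros, while ANB020 tolerators are rechallenged and can show real symptoms. The error differs by arm and works against ANB020.

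This is distinct from absent Day 45 values. Here a value exists but does not measure the endpoint, and Section 17.3.3 would report a confidence interval and p-value built on it.

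**Working it through.** **No figure to reproduce.** The documents give no effect size, SD, reaction rate or mean OFC score, and Protocol Section 9.1 says the sample size is not based on power. Only the allocation is fixed: 15 ANB020 and 5 placebo (Section 6.2.2). All other inputs below are assumptions.

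**Step 1. Algebra.** Let pA and pP be the shares reacting at Day 14 on ANB020 and placebo. Let R and T be the mean Day 45 scores under peanut in Day 14 reactors and tolerators, taken as equal across arms. Let u be the share of reactors not rechallenged and scored 0.

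- True difference = (pA − pP)(R − T)
- Observed difference = (pA − pP)((1 − u)R − T)
- Share of the effect lost = uR/(R − T)
- The sign reverses when (1 − u)R < T, that is, u > 1 − T/R

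With pA = 0.6, pP = 1.0, R = 8, T = 3:

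| u | Calculation | Difference |
|---|---|---|
| 0 | −0.4 × (8 − 3) | −2.0 |
| 0.25 | −0.4 × (6 − 3) | −1.2 |
| 0.50 | −0.4 × (4 − 3) | −0.4 |
| 0.75 | −0.4 × (2 − 3) | +0.4 |
| 1 | −0.4 × (0 − 3) | +1.2 |

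The reversal point is 1 − 3/8 = 0.625. It is 0.75 for T = 2 and 0.375 for T = 5. With T = 0, half the effect is lost at u = 0.5 and all of it at u = 1, but it never reverses.

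**Step 2. A threshold model.** Assume a lognormal reaction threshold with median 60 mg and log-SD 1.0, limited to below 500 mg (the maximum cumulative dose in Section 6.1.1). Assume visit-to-visit log-SD 0.4, and a mean score of 6 when reacting and 0 otherwise. Simulated mean Day 45 scores:

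| Threshold gain on ANB020 | All challenged | Every Day 14 reactor scored 0 |
|---|---|---|
| none (placebo) | 5.93 | 0.05 |
| 3-fold | 5.05 | 0.33 |
| 5-fold | 4.16 | 0.46 |
| 8-fold | 3.15 | 0.52 |

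Subtracting the placebo row gives the columns u = 0 and u = 1 below. The difference is linear in u, so the rest follows by interpolation. The reversal point is |d0|/(|d0| + d1), where d0 and d1 are the differences at u = 0 and u = 1.

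| Gain | u = 0 | u = 0.5 | u = 0.75 | u = 1 | Lost at u = 0.5 | Reversal point |
|---|---|---|---|---|---|---|
| 3-fold | −0.88 | −0.30 | −0.01 | +0.28 | 66% | 0.88/1.16 = 0.76 |
| 5-fold | −1.77 | −0.68 | −0.14 | +0.41 | 62% | 1.77/2.18 = 0.81 |
| 8-fold | −2.78 | −1.16 | −0.34 | +0.47 | 58% | 2.78/3.25 = 0.86 |

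**Step 3. At the planned size.** ANCOVA of Day 45 change with 15 and 5 patients, 6,000 runs per setting, Step 1 inputs, unprovoked mean 0.2. With complete Day 45 data this matches the SAP's repeated-measures model with unstructured covariance and baseline-by-visit.

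| u | Mean difference | Estimate favours placebo | Significantly favours placebo |
|---|---|---|---|
| 0 | −1.98 | 6% | 0.0% |
| 0.5 | −0.42 | 43% | 2.5% |
| 0.75 | +0.35 | 60% | 3.8% |
| 1 | +1.14 | 98% | 5.8% |

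**Step 4. If unprovoked scores are left out.** If no reactor is rechallenged, placebo has no usable Day 45 score when all 5 react. The chance is pP⁵: 0.17, 0.33, 0.59 and 1.00 for pP = 0.7, 0.8, 0.9 and 1.0.

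**The case against.** **The table evidence is weak.** Superscripts in the extracted table are unreliable. Footnote l appears on the screening FSH cell, where a rule about Day 14/15 reactions makes no sense, and some l marks may be misread j. This stands: the missing footnote must be checked against the PDF. The SAP gap does not depend on it.

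**The text ties scoring to a challenge.** A reader might infer that Section 4.1 independently asks every patient for a Day 45 score. It does not. Its symptom-monitoring sentence sits within a description of how the optional challenge is run, next to the stopping rule and the recording of tolerated dose. Sections 6.1.1, 6.2.5 and 7.1.3 point the same way, and the exploratory objective concerns symptoms to peanut challenge. Sites following the text may record nothing.

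**Entry into the model is not established.** A reader might infer that unchallenged reactors necessarily enter the Day 45 model. The SAP does not settle this. If a post-challenge score is analysed, these patients are missing. If the score before the first challenge is used, as the baseline row of Table 14.2.2.1 suggests, everyone's score is unprovoked and the reactor-specific bias does not arise. SAP Section 6 also keeps extra measurements out of descriptive statistics, but says nothing on models, and Day 45 is a scheduled visit. What stands is that entry is possible, not certain.

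**The consequence is limited.** The endpoint is exploratory, only 5 placebo patients are planned, and Protocol Section 2.3 disclaims hypothesis testing. This bears on priority. SAP Section 17.3.3 nonetheless plans a p-value for this comparison.

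**Conclusion.** The concern holds as a gap that can produce bias, not as a bias shown to occur. It requires that a score is recorded without a challenge and that the analysis admits it. Table 4.1 as extracted allows the first, and nothing in SAP Section 17.3.3 prevents the second.

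If both happen, the Day 45 OFC comparison is biased against ANB020. With half of the reactors unchallenged, the threshold model loses 58 to 66% of the effect and the Step 1 example loses 80%. A reader might infer that the effect would simply reverse. The documents do not support that: rechallenge is discretionary, no rechallenge rate is given, and reversal needs u > 1 − T/R. That is 76 to 86% of reactors in the threshold model and 62.5% in the Step 1 example, and it never happens if tolerators score 0. Even with no reactor rechallenged, a significant result for placebo was uncommon in the planned-size case (5.8%).

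All sizes rest on assumed thresholds, scores and reaction rates. The Day 14 primary and secondary endpoints are not affected.

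**What to change.** 1. **Protocol.** Check the Day 45 OFC cell against the PDF. Reconcile Table 4.1 with Sections 6.1.1, 6.2.5 and 7.1.3 on whether the tool is scored when no challenge is given.
2. **SAP.** Update the reference protocol to Amendment 5. In Section 17.3.3 and Tables 14.2.2.1 and 14.2.3.1, use a Day 45 OFC score only where "Was oral BPCFC performed" is Yes and peanut was given. Name one post-peanut time point and use it at baseline, Day 14 and Day 45. List any other Day 45 score only.
3. **Reporting.** State in advance that if too few placebo scores remain, the Day 45 OFC contrast is reported descriptively or as not estimable.

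The cost is a table clarification and an SAP filter on a field already in the listing shell, with no added procedure. The downside is sparse Day 45 OFC data, possibly with no placebo values (Step 4). The excluded scores carry no information on response to peanut. The filter does not solve the remaining problem that challenged patients are selected by their Day 14 outcome, and the report should say so.
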